We have developed Contralaterally Controlled Functional Electrical Stimulation (CCFES), an innovative neuromuscular electrical stimulation (NMES) treatment for improving the recovery of hand function after stroke. Hand CCFES stimulates the paretic hand to open in proportion to the degree of volitional opening of the contralateral unimpaired hand. This enables the stroke survivor to perform active repetitive hand opening exercises, hand motor-control tasks, and functional tasks with the paretic hand. In this study, we add stimulation of elbow extensors controlled by the contralateral elbow in order to improve reach as well as hand opening. The purpose of this study is to maximize the treatment effect of CCFES by adding stimulated elbow extension. The specific aims are to (1) estimate the effect of Arm+Hand CCFES on upper limb motor impairment and activity limitation, (2) estimate the effect of adding stimulated elbow extension to Hand CCFES, and (3) define the relationship between treatment effect and time elapsed between stroke onset and start of treatment. Stroke survivors with upper limb hemiplegia (≤ 2 years) will be randomly assigned to receive 12 weeks of either Arm+Hand CCFES (stimulates elbow extension and hand opening), Hand CCFES (stimulates hand opening), or Arm+Hand Cyclic NMES (stimulates elbow extension and hand opening but with pre-set timing and intensity, i.e., not intention-driven), plus lab-based therapist-guided task practice. Upper limb impairment and activity limitation will be assessed at baseline, 6, 12, 20, 28, and 36

weeks.

This is the first randomized controlled trial of Arm+Hand CCFES in subacute upper extremity hemiplegia. Ultimately, the information learned in this study will serve to accelerate the development of a new treatment for reducing post-stroke disability.

Specific Aims

AIM 1: Estimate the effect of Arm+Hand CCFES on upper limb motor impairment and activity limitation.

Hypothesis 1: Stroke survivors treated with Arm+Hand CCFES have better outcomes on upper limb impairment and activity limitation measures than those treated with dose-matched Arm+Hand Cyclic NMES.

AIM 2: Estimate the effect of adding stimulated elbow extension to Hand CCFES.

Hypothesis 2: Stroke survivors treated with Arm+Hand CCFES will have greater reductions in upper limb impairment and activity limitation than those treated with Hand CCFES.

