AIM 3: Describe the relationship between treatment effect and time elapsed between stroke onset and start of treatment.

Hypothesis 3: Patients who start Arm+Hand CCFES sooner after their stroke achieve better outcomes.

Methods and Procedures

The study includes three treatment groups: 1) Arm+Hand CCFES, 2) Hand CCFES, 3) Arm+Hand Cyclic NMES. The two CCFES groups will use a stimulator that activates the muscles of the paretic upper limb in response to and with an intensity proportional to movement of the contralateral arm and/or hand. This is in contrast to the Cyclic NMES, which delivers stimulation automatically and repeatedly with preprogrammed timing and intensity. For the Hand CCFES group, paretic finger and thumb extensors will be stimulated; for the Arm+Hand CCFES and Arm+Hand Cyclic NMES groups, both the elbow and hand extensors will be stimulated. The treatment dose will be equivalent for all

groups - approximately 2 hrs per day of self-administered stimulation-mediated exercise at home plus 70 min of functional task practice twice a week in the laboratory for 12 weeks.

Subjects will be assigned to one of the 3 treatments using an adaptive randomization algorithm to minimize group imbalances on: (1) time post-stroke (< 90 days vs. \geq 90 days), (2) baseline motor status (moderate vs. severe), and (3) whether or not the pre-stroke dominant side is the paretic side. Patients with at least 10° active wrist extension, 10° active thumb abduction/extension, and 10° active extension in at least two additional digits will be considered to have "moderate" impairment, and patients with less movement than this who meet all the other motor criteria will be considered to have "severe" impairment.

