Compliance with home stimulation will be monitored with diaries and electronic data-logging. Every week, participants will be given a diary to log completion of exercise sessions. Also, the stimulator will log the date and time the unit is turned on and off and the date and time of start and completion of an exercise session. The diary will be collected weekly and compared with usage data from the stimulator in the presence of the participant at the beginning of each lab session.

Most subacute stroke patients have multiple rehabilitation needs that require intervention in addition to the study intervention. Therefore, to account for the potential confounding effect of concomitant therapies, the total number of hours of physical and occupational therapy sessions will be monitored during the entire study period. Any group imbalance in concomitant therapy will be adjusted for in the statistical analysis. The use of electrical stimulation or other experimental procedures involving the hemiparetic upper limb, changes in spasticity medication, Botulinum toxin injections to upper limb muscles, intrathecal baclofen, use of an arm sling, and use of a resting hand splint will be discouraged unless they are absolutely necessary.

All subjects will undergo assessments of upper limb impairment and activity limitation by a blinded assessor prior to treatment and at 6, 12, 20, 28, and 36 weeks. The assessments will be completed in two separate sessions (less than 7 days apart) lasting < 2 hrs each in order to avoid possible fatigue effects. Participants will receive an incentive payment of \$25 when they complete each set of follow-up assessments (i.e., at 20, 28, and 36 weeks for a total of \$75 per participant).

Outcome Measures

All subjects will undergo assessments of upper extremity impairment and activity limitation by a blinded assessor prior to treatment and at 6, 12, 20, 28, and 36 weeks (unless otherwise specified below). In addition, at the 12-week assessment a questionnaire will be given regarding device usability, treatment dosage, and treatment effectiveness. The assessments will be completed in two separate sessions (less than 7 days apart) lasting < 2 hrs each in order to avoid possible fatigue

effects. The outcome measures and procedures are:

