We hypothesized that participants treated with A+H CCFES would have greater improvements in upper extremity motor function from baseline to 6-months post-treatment than participants treated with Hand CCFES or A+H cNMES. The distributions of baseline characteristics were compared in the three groups by nonparametric Kruskal-Wallis tests or Fisher's Exact tests, as appropriate, with a significance level of 0.05. For each outcome measure, we used a mixed effects modeling approach evaluating fixed effects for group, time and group by time interaction and a random intercept and slope. Least square (LS) means, calculated using model estimates and adjusted for missing values, were computed for each group at each time point. We used differences of LS means from baseline to 6 months post-treatment to estimate the within-group mean changes and between-group differences in change. We calculated 95% confidence intervals (CIs) for these point estimates; standard errors for LS means are adjusted for model covariance parameters. CIs that do not contain zero were considered to be indicative of significant changes. Effect size (Cohen d) estimates were calculated as the between-group difference in outcome variable mean divided by the common standard deviation of the outcome variable. Secondly, we hypothesized that participants who were <90 days post-stroke or had moderate hand impairment at baseline would improve more than subjects who were >90 days post-stroke or had severe hand impairment at baseline. We used a similar mixed effects modeling approach with analysis of LS means to test these secondary hypotheses for each outcome across all participants and within each group.

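### Aim 3 asks how the treatment effect varies with time since stroke, but the SAP plans only early-versus-late comparisons (pooled and within arm) and no between-arm contrast by time since stroke

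*Combined protocol and SAP*

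**What the plan says.** The Abstract states the third aim as to "define the relationship between treatment effect and time elapsed between stroke onset and start of treatment", and Specific Aims repeats it: "AIM 3: Describe the relationship between treatment effect and time elapsed between stroke onset and start of treatment". Hypothesis 3, directly below, reads "Patients who start Arm+Hand CCFES sooner after their stroke achieve better outcomes". It names no comparison arm. Hypotheses 1 and 2, by contrast, set Arm+Hand CCFES against Cyclic NMES and against Hand CCFES.

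The Statistical Analysis Plan turns the third aim into the hypothesis that "participants who were <90 days post-stroke or had moderate hand impairment at baseline would improve more than subjects who were >90 days post-stroke". It then uses a similar mixed model "to test these secondary hypotheses for each outcome across all participants and within each group". The main model has group, time and their interaction. Time there means assessment visit, because LS means are computed for each group at each time point. The only between-arm contrast described is the overall difference in change from baseline to 6 months post-treatment.

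Two further places matter. Methods and Procedures assigns patients by an "adaptive randomization algorithm to minimize group imbalances on: (1) time post-stroke", split at 90 days. On concomitant therapy it says: "Any group imbalance in concomitant therapy will be adjusted for in the statistical analysis".

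**The concern.** Aim 3 and Hypothesis 3 ask different questions, and the SAP follows the hypothesis. Whether patients treated early improve more than patients treated late is a question of prognosis. Whether the advantage of Arm+Hand CCFES over another arm is larger in early patients is a question of effect modification, and this is what Aim 3 asks if effect means what it means in Hypotheses 1 and 2.

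Time since stroke is not randomised. Early and late patients may recover at different rates whatever they receive. The SAP treats a CI that excludes zero as significant, so a positive early-late result, pooled or within the Arm+Hand CCFES arm, could be reported as showing that the treatment works better when started sooner, when background recovery alone could produce it. The planned adjustment for concomitant therapy does not help, because it addresses imbalance between arms and not between early and late patients.

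**Working it through.** **What each comparison estimates.** Let B be the early-minus-late difference in change that would occur in any arm (background recovery). Let M_k be the further early-late difference due to the treatment in arm k (A = Arm+Hand CCFES, C = Cyclic NMES).

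- Within arm A: B + M_A.
- Pooled over three equal arms: B + (M_A + M_H + M_C)/3, where H = Hand CCFES.
- Between arms: (B + M_A) − (B + M_C) = M_A − M_C.

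B cancels only in the third line, which the SAP does not specify. Separate within-arm results let a reader compare two gaps by eye, but they give neither the difference between the gaps nor its CI.

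**Inputs for an illustration.** The documents state no sample size, SD, early share or recovery gap, so there is no figure to reproduce. All of the following are assumptions: total N = 60, 90 or 120 in three equal arms; early share f = 40% or 50%, with 25% as a sensitivity; B = 0.3 or 0.5 in units of the SD of change.

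**Standard errors (SD units), with n = N/3.**

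- Within arm: √(1/(nf) + 1/(n(1−f))). For N = 60, f = 0.4: √(1/8 + 1/12) = 0.456.
- Pooled: the same with N in place of n: √(1/24 + 1/36) = 0.264.
- Between-arm interaction: √2 × 0.456 = 0.645, which is 1.41 times the within-arm SE and √6 = 2.45 times the pooled SE.

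**Background recovery only (every M_k = 0).** Probability that a two-sided 5% test is significant in favour of early patients (noncentral t, noncentrality B/SE):

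| B | Early share | Pooled, N = 60 to 120 | Within arm, N = 60 to 120 |
|---|---|---|---|
| 0.3 | 40-50% | 0.20-0.37 | 0.09-0.15 |
| 0.5 | 40-50% | 0.46-0.78 | 0.18-0.34 |
| 0.5 | 25% | 0.38-0.65 | 0.15-0.27 |

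Without any gap these probabilities would be 0.025. For the interaction, 20,000 simulated trials in each of 12 settings (both gaps, three N, 40% and 50% early) gave two-sided rejection rates of 0.046-0.053. That is about 0.025 in the direction counted in the table, so the background gap does not inflate it.

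**Effect modification only (B = 0, M_A = 0.5, 40% early).** The simulated within-arm test is significant with probability 0.180, 0.257 and 0.326 at N = 60, 90 and 120. Background recovery alone, with B = 0.5, gives 0.178, 0.253 and 0.326. The within-arm test therefore cannot tell the two explanations apart.

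**Precision of the missing contrast.** The 95% CI half-width is t(0.975, N−6) × SE. For N = 60, f = 0.4: 2.005 × 0.645 = 1.29. Over 40-50% early it is 1.27-1.29 at N = 60, 1.03-1.05 at N = 90 and 0.89-0.90 at N = 120. At 25% early it is 1.46, 1.19 and 1.02. Power for a 0.5 SD modification at 40% early is 0.118, 0.158 and 0.189.

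**The case against.** The SAP does test Hypothesis 3 as worded: the within-group analysis includes the Arm+Hand CCFES arm, and the hypothesis names no comparator. Aim 3 only sets out to describe a relationship, and treatment effect could be read as the outcome in treated patients. The phrase about a similar modelling approach does not list its terms, so a joint model with a three-way interaction is not ruled out. The aim is third in order, the hypothesis is secondary, and the contrasts for Aims 1 and 2 are untouched. The added contrast would be imprecise. Because both comparators are active, it would be near zero if timing affects all three arms alike.

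Much of this stands. Hypothesis 3 is met, the stakes are limited to Aim 3, and the contrast shows modification only relative to other stimulation. The rest does not remove the problem. Hypotheses 1 and 2 are comparative, so a between-arm reading of effect is the more natural one. Whatever terms the model contains, the only outputs named are pooled and within-arm. A descriptive aim still calls for an estimate with its CI, even a wide one.

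**Conclusion.** The concern holds. Followed as written, the plan cannot separate background recovery from variation in treatment effect, so Aim 3 has no matching estimate. This conclusion rests on the text and does not depend on any assumed number. The size does: under the assumed ranges with 40-50% early, background recovery of 0.3 to 0.5 SD with no effect modification yields a positive pooled finding with probability 0.20-0.78 and a positive within-arm finding with probability 0.09-0.34. With fewer early patients these figures fall. The point should be fixed. It does not affect the overall between-arm comparisons.

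**What to change.** - For Aim 3, add group by visit by time-since-stroke terms, with all lower-order terms, to the mixed model. Use the randomisation strata (<90 versus ≥90 days); the SAP's <90 versus >90 leaves day 90 unassigned.
- Report Arm+Hand CCFES minus Cyclic NMES, and Arm+Hand CCFES minus Hand CCFES, for change at 6 months post-treatment in each stratum. Report the difference between strata with a 95% CI.
- Give continuous days since stroke as a supportive analysis.
- Keep the pooled and within-arm early-late comparisons, labelled prognostic and not as evidence that the treatment effect depends on timing. The moderate-versus-severe comparison may stay as a prognostic hypothesis.
- Reword Aim 3 or Hypothesis 3 so that the two ask the same question.
- The SAP is written in the past tense. If analysis has already begun, mark the contrast as added later.

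The cost is SAP wording and one three-way interaction. No new data are needed, since time since stroke is already an allocation factor. The downside is low precision and power, as shown in the working, so the result may be inconclusive and should be presented as an estimate relative to active comparators.

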as lasting 12 weeks, the 6-week (mid-treatment) assessments will take place during their own week, resulting in an overall Treatment Period of 13 weeks: 6 weeks of treatment with home stimulation + lab therapy sessions, a week during which the mid-treatment assessments take place, and 6 more weeks of treatment with home stimulation + lab therapy sessions. During the mid-treatment assessment week, subjects may still undergo home stimulation exercise, with the limitation that they not do so during the 24-hour period preceding a lab assessment visit.

There are a total of 40 visits involved in this study; 2 are home visits, 38 are visits to the lab.

Visit 1. Consent and eligibility (2 hrs)

Visit 2. Baseline Assessment 1 (2 hrs)

Visit 3. Baseline Assessment 2 (2 hrs)

Visit 4. Randomization, Device Setup and Training (2.5 hrs)

Visit 5. Home equipment setup (2 hrs)

The treatment period for all 3 groups will be 13 weeks in duration (12 weeks of defined treatment + mid-treatment assessments during week 7), with the defined treatment consisting of two components:

- 1) Therapist-guided task practice performed twice a week (70-min each) in the research laboratory.
- 2) Self-administered stimulation-mediated exercise performed 10 sessions (46-60 min each) per week at home. Also, all participants will be encouraged to use their affected hand to perform tasks at home as much as possible in order to overcome "learned non-use" by creating a habit of using the affected hand."

Visits 6-17. Therapist-Guided Task Practice. (Treatment: Weeks 1-6)

Visit 18. 6-Week Outcome Assessment 1 (Mid-treatment: Assessment week 7)

Visit 19. 6-Week Outcome Assessment 2 (Mid-treatment: Assessment week 7)

Visits 20-31. Therapist-Guided Task Practice. (Treatment: Weeks 8-13)

Visit 32. Home equipment pickup (30 min)

Visit 33. 12-Week Outcome Assessment 1 (End of treatment: Week 14)

Visit 34. 12-Week Outcome Assessment 2 (End of treatment: Week 14)

Visit 35. 20-Week Outcome Assessment 1 (2 months post-treatment)

Visit 36. 20-Week Outcome Assessment 2 (2 months post-treatment)

Visit 37. 28-Week Outcome Assessment 1 (4 months post-treatment)

Visit 38. 28-Week Outcome Assessment 2 (4 months post-treatment)

Visit 39. 36-Week Outcome Assessment 1 (6 months post-treatment)

Visit 40. 36-Week Outcome Assessment 2 (6 months post-treatment)

Selection Criteria

Inclusion Criteria

- Age ≥ 21 and ≤ 80
- ≤ 2 years of first clinical hemorrhagic or nonhemorrhagic stroke

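### Aim 3 asks how treatment effect relates to time since stroke, but the SAP only compares two classes split at 90 days, which gives no estimate of that relationship

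*Combined protocol and SAP*

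**What the plan says.** Specific Aims: "AIM 3: Describe the relationship between treatment effect and time elapsed between stroke onset and start of treatment". The Abstract gives the same aim with the verb define in place of describe. The attached hypothesis is directional, concerns one arm and names no cut-point: "Hypothesis 3: Patients who start Arm+Hand CCFES sooner after their stroke achieve better outcomes".

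Selection Criteria: a participant may enter at "≤ 2 years of first clinical hemorrhagic or nonhemorrhagic stroke", so time since stroke can run to about 730 days.

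Methods and Procedures: the first minimisation factor begins "time post-stroke (< 90 days vs", and its other class is 90 days or more. Day 90 therefore falls in the later stratum.

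Statistical Analysis Plan: the later class in the secondary hypothesis is defined as "subjects who were >90 days post-stroke or had severe hand impairment at baseline", so day 90 is left out of it. The early class is everyone below 90 days, and the SAP expects this class to show the larger improvement. The hypothesis is tested with a mixed model and LS means like those of the main analysis, for each outcome, once over all participants and once inside each arm. The SAP describes neither a continuous time-since-stroke term nor an interaction of treatment group with time since stroke.

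**The concern.** A relationship with elapsed time needs an estimate that varies with time. A two-class contrast gives one difference. It treats a patient at day 91 like one at day 700, and puts patients at days 89 and 91 in opposite classes. It yields no slope, no curve and no predicted change at any given time since stroke, so the aim as worded would not be met even if the comparison were significant.

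Power is also at stake. If outcome changes gradually with time since stroke, replacing days by a yes/no indicator discards information. Hypothesis 3 concerns one of three arms, so its within-arm test has the fewest participants to spare.

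The two 90-day definitions also differ at the boundary. A participant at exactly day 90 has a minimisation stratum but, as the SAP is written, no analysis class.

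**Working it through.** **Nothing to reproduce.** The documents state no sample size, power or efficiency figure for this question.

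**Inputs from the documents.** The cut is at 90 days and the upper entry limit is 2 years (730 days). The onset date must be known, because both the entry limit and the minimisation factor depend on it, although no passage says that days are recorded.

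**Assumed inputs.** Earliest entry is day 14; entry times are log-uniform or uniform on 14 to 730 days; the effect is linear in log days or in days.

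**Measure.** If outcome is linear in x, the efficiency of the indicator I(t < 90) relative to x is RE = corr(x, I)². The loss is 1 − RE. For any x,

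RE = p(1 − p)(m₁ − m₀)² / Var(x),

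where p is the share before day 90 and m₁, m₀ are the class means of x. If x is uniform this reduces to 3p(1 − p), which is at most 0.75, at p = 0.5.

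**1. Log-uniform entry, linear in log days.** p = ln(90/14)/ln(730/14) = 1.861/3.954 = 0.471. RE = 3 × 0.471 × 0.529 = 0.75. Loss 25%.

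**2. Uniform entry, linear in log days.** p = 76/716 = 0.106, so p(1 − p) = 0.0949. Mean log days is 3.843 before day 90 and 5.887 after, a difference of 2.045. The variance of log days is 0.688. RE = 0.0949 × 2.045²/0.688 = 0.58. Loss 42%.

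**3. Uniform entry, linear in days.** RE = 3 × 0.106 × 0.894 = 0.28. Loss 72%.

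**4. Log-uniform entry, linear in days.** RE = 0.51. Loss 49%.

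**Power.** If the continuous term had 80% power, the split would have Φ(√RE × (1.960 + 0.842) − 1.960):

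| RE | Loss | Power with the split |
|---|---|---|
| 0.75 | 25% | 68% |
| 0.58 | 42% | 57% |
| 0.51 | 49% | 51% |
| 0.28 | 72% | 32% |

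**Sensitivity to the assumptions** (simulated, about 1,000,000 draws each, truncated at 730 days):

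- Other uniform, exponential (mean 90 to 365) and lognormal (median 60 to 150) entry distributions: loss 30% to 57% if linear in log days, 25% to 78% if linear in days.
- Later-centred entry loses more. With a lognormal median of 250 days and log-SD 0.5, only 2% enter before day 90 and the loss in log days is 87%.
- Two separated clusters of entry times (means 30 to 45 days and 180 to 540 days): loss 5% to 19% in log days, 3% to 26% in days.
- A true step at 90 days: loss 0%. RE is symmetric, so in cases 1 and 2 a log-days term would then lose the same 25% to 42%.
- An effect that decays and levels off (decay constant 30 to 90 days): r² is 0.54 to 0.79 for the split, 0.23 to 0.66 for a straight line in raw days and 0.61 to 0.97 for log days. Raw days can do worse than the split; log days did at least as well in each of these cases.

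**Day 90.** The expected number at exactly day 90 is N × P(day 90). With an assumed N of 60 to 150 and a probability of 1/730 to 1/100, this is 60/730 = 0.08 up to 150/100 = 1.5 participants.

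**The case against.** The 90-day cut is not data-driven. It is a minimisation factor, fixed before allocation and balanced across arms, and analysing by an allocation factor is ordinary practice. Hypothesis 3 is only directional, and an early-versus-late comparison does test a direction. The SAP also runs the comparison over all participants, so the question does not rest on one arm alone. All of this stands. It defends the split as a test of direction, but not as a description of a relationship, which is what Aim 3 asks for.

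A reader might infer that the split necessarily costs a quarter or more of the information. The documents do not support that. They give no entry distribution and no effect shape; a step at 90 days is monotone and costs nothing, and clustered entry can cost a few per cent.

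A reader might also take the day-90 gap as a substantive flaw. It probably affects one participant or none, and the minimisation factor already shows where that participant belongs.

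Finally, a continuous term fitted in the Arm+Hand CCFES arm alone would not answer Aim 3 either. Without a comparator it describes change by time since stroke, with spontaneous recovery mixed in. This objection is correct, and the fix has to meet it.

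**Conclusion.** The mismatch between aim and analysis holds without assumptions: Aim 3 asks for a relationship over entry times of up to 2 years, and the SAP offers only a two-class comparison.

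The size of the information loss is conditional. It is about 25% to 42% if the effect is roughly linear in log days and entry is log-uniform or uniform from day 14 to day 730, and up to about 72% if it is linear in days. These are illustrations and not bounds: other single-peaked entry patterns can lose more, bimodal entry less, and a true step at 90 days nothing.

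The boundary difference is a wording correction only. The point concerns a secondary hypothesis and leaves the main between-arm comparisons untouched. It should be changed, because the remedy is cheap and the aim is otherwise not answered as worded.

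**What to change.** For Hypothesis 3, add days from stroke to start of treatment as a continuous term: log days, named in advance, interacting with visit, and with a check for curvature such as a spline. Fit it within the Arm+Hand CCFES arm and across all participants. Report predicted change from baseline to 6 months post-treatment with 95% CIs at several times inside the observed range, for example 30, 90, 180 and 365 days.

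Label the within-arm result as change by time since stroke. For any statement about treatment effect, add the group-by-log-days term (by visit) to the model of all participants and report the between-arm difference at the same times.

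Keep the 90-day comparison as a secondary display, which also guards against a threshold near 90 days. Change its later class from above 90 to 90 days or more, to match the minimisation factor.

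Cost: SAP wording and a few extra model fits. No new data should be needed, since eligibility and minimisation already require the onset date. The downside is that a functional form must be chosen in advance. The SAP is written in the past tense; if the analysis has already been run, the new model must be labelled post hoc.
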